	
 
WaveCrest arm subjects discontinuing clopidogrel (or P2Y12 inhibitor) must remain on 75-100mg aspirin daily indefinitely.
 
 
6 months post-implant
 
 
Subjects with peri-device flow >5mm at 45 days will undergo a TEE at 6 months.
 
Watchman arm subjects discontinuing warfarin and clopidogrel (or P2Y12 inhibitor) should take daily aspirin per the Watchman DFU indefinitely.
 
																																																																		
Number of Trial Sites	Up to 100 sites will participate in the trial in North America, Europe, Australia, and Asia																																																																		
Sample Size	
 
Up to 1,550 subjects will be randomized in a 1:1 ratio between the WaveCrest and Watchman devices. The trial design offers at least 80% power to establish non-inferiority for the effectiveness and safety hypotheses across the range of possible event rates.
 
Sites will be allowed up to 5 roll-in cases (up to 2 per operator) prior to randomization for a total of up to 500 roll-in subjects.
 
Up to 2,050 total subjects will be enrolled
 
																																																																		
Enrollment Phase	The enrollment phase is expected to last between 2 and 3 years.																																																																		

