## Clinical Experience with Watchman Device

	Title: The WAVECREST 2 Trial  Clinical Investigational Plan	Doc. #: CHX_IP014	Rev: H
---	--	-----------------------------	------------------

The largest body of clinical experience on the Watchman device is from the PROTECT-AF IDE trial, which randomized 707 subjects with non-valvular AF in a 2:1 ratio between intervention (i.e., Watchman device, n = 463) and control (i.e., warfarin, n = 244). Subjects who received the intervention were required to be on warfarin for 45 days post-implant or until the LAA was closed followed by clopidogrel up to 6 months post-implant and aspirin indefinitely, whereas the control group was required to continue warfarin for the duration of follow-up. Effectiveness was assessed by a primary composite endpoint of stroke, cardiovascular death or systemic embolism. The trial was designed to demonstrate non-inferiority of the intervention to the control group. Trial participants were elderly (~72 years old) with approximately 70% having CHADS2 score of ≥ 2. At 1,065 subject-years of follow-up, the primary endpoint (composite of stroke, systemic embolism or cardiovascular death) event rate was 0.03 per subject-year in the intervention group and 0.049 per subject-year in the control group. The trial met its endpoint, demonstrating non-inferiority of the intervention. However, there was a higher rate of safety events (major bleeding, pericardial effusion, device embolization) in the intervention group than in the control group, primarily due to peri-procedural complications. Additionally, there were confounding effects of concomitant antithrombotic use and subjects not receiving the assigned treatment as randomized. The trial also enrolled some subjects who did not have a strong indication for warfarin (CHADS2 score = 1). After 1,588 subject-years of follow-up, the primary effectiveness event rates remained lower in the intervention group (0.03 per subject-year) than the control group (0.043 per subject-year). However, the rate of primary safety events remained higher in the intervention group than in the control group (0.055 versus 0.036 per subject-year). A second IDE trial (PREVAIL) was designed to study subjects at higher risk of stroke and excluded subjects who were not indicated for chronic clopidogrel therapy. The trial was designed with 2 co-primary effectiveness endpoints and 1 co-primary safety endpoint. The trial enrolled subjects with a CHADS2 score of ≥ 2 or subjects with a CHADS2 score of 1, who also had other risk factors for stroke (effectively CHA2DS2-VASc = 2). A total of 407 subjects were randomized (intervention: n = 269, control: n = 138). In a Bayesian analysis, the 18-month primary endpoint event (composite of stroke, systemic embolism or cardiovascular death) rates were 0.064 in the intervention group and 0.063 in the control group. The 18-month event rate for the second primary endpoint of ischemic stroke or systemic embolism beyond 7 days post-randomization occurred at a rate of 0.0253 subject-years in the intervention group and 0.020 in the control group. The third primary endpoint (composite of death, ischemic stroke, systemic embolism, or device or procedure-related events requiring open cardiac surgery or major endovascular intervention) within 7 days of randomization occurred in 2.2% of subjects in the intervention group. The trial met two of the three primary endpoints (i.e., second and third primary endpoints). In a pooled subject-level meta-analysis combining the PROTECT AF and PREVAIL datasets (recently presented at an FDA Advisory Panel meetingb), the Watchman device was associated with:

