### 4.3 Endpoints

#### 4.3.1 Primary Endpoint

This trial is designed to evaluate the safety and effectiveness of the Coherex WaveCrest LAA occlusion device to the Boston Scientific Watchman LAA occlusion device by demonstrating that the device is non-inferior to the Watchman Device with respect to the primary safety and effectiveness endpoints. If non-inferiority is demonstrated, superiority will be evaluated.

- The primary effectiveness endpoint is the composite rate of ischemic stroke or systemic embolism at 24 months.
- The primary safety endpoint is the composite rate of all cause death; procedure- or device-related complications requiring percutaneous or surgical intervention, including embolization of a LAA closure device, drainage of pericardial effusion, or repair of cardiac or vascular structures through 45 days post-procedure; or major bleeding.

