## 15. STATISTICAL METHODS

This section summarizes the statistical methods for the WAVECREST 2 clinical trial. A detailed statistical analysis plan describing the sample size calculations and detailed statistical methods that will be applied to the data collected in this trial will be contained in a separate document entitled **Statistical Analysis Plan** which supersedes this summary. This document will be finalized prior to un-blinding of the database and any analysis of the data

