### 15.4 Primary Effectiveness Endpoint

The primary effectiveness endpoint for WAVECREST 2 is the 24-month rate of ischemic stroke or systemic embolism.

[REDACTED]

 	Title: The WAVECREST 2 Trial  Clinical Investigational Plan	Doc. #: CHX_IP014	Rev: H
--	--	-----------------------------	------------------

Let  $p_{\text{WAVECREST}}$  be the primary effectiveness endpoint rate at 24 months in the device arm, while  $p_{\text{CONTROL}}$  is the corresponding rate in the control arm. Specifically, the following null and alternative hypotheses will be tested:

$$H_0: p_{\text{WAVECREST}} / p_{\text{CONTROL}} \geq 1.75$$

$$H_a: p_{\text{WAVECREST}} / p_{\text{CONTROL}} < 1.75$$

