8.3 Primary Effectiveness Endpoint

The primary effectiveness endpoint is the composite rate of ischemic stroke or systemic embolism.

[REDACTED]

Let $p_{\text{WAVECREST}}$ be the primary effectiveness endpoint rate at 24 months in the device arm, while p_{CONTROL} is the corresponding rate in the control arm.

[REDACTED]

[REDACTED]
[REDACTED]
[REDACTED]
[REDACTED]
[REDACTED]

[REDACTED]

[Redacted text block]

[Redacted]	}	[Redacted]	[Redacted]	}	[Redacted]
		[Redacted]	[Redacted]		[Redacted]
		[Redacted]	[Redacted]		[Redacted]
		[Redacted]	[Redacted]		[Redacted]
		[Redacted]	[Redacted]		[Redacted]
		[Redacted]	[Redacted]		[Redacted]

[Large redacted text block]

[Redacted text block]

[REDACTED]

[REDACTED]

[REDACTED]

If non-inferiority is established for both the primary safety, the primary effectiveness endpoints and the second secondary effectiveness endpoint, the primary safety endpoint will then be tested for superiority, and if superiority is established for the primary safety endpoint, then the primary effectiveness endpoint will be tested for superiority. The following null and alternative hypotheses will be tested:

$$H_0: p_{\text{WAVECREST}} - p_{\text{CONTROL}} \geq 0.0\%$$

$$H_a: p_{\text{WAVECREST}} - p_{\text{CONTROL}} < 0.0\%$$

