8.5 Sample Size and Power

A minimum sample size of 1250 subjects will be randomized in the trial up to a maximum of 1550 randomized subjects.

[REDACTED]

[REDACTED]

- [REDACTED]
- [REDACTED]
- [REDACTED]
- [REDACTED]

[REDACTED]

[figure not shown]
[Redacted text block]

[Redacted text block]

[Redacted text block]

[Redacted text block]

[Large redacted text block]

[Redacted text block]

[Large redacted text block]

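### Is the promised 80% power for effectiveness out of reach at the Watchman event rate that the protocol itself quotes?

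*Protocol*

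**What the plan says.** Protocol section 1 (Synopsis, Sample Size) says "Up to 1,550 subjects will be randomized in a 1:1 ratio between the WaveCrest and Watchman devices" and then makes the power claim: "The trial design offers at least 80% power to establish non-inferiority for the effectiveness and safety hypotheses across the range of possible event rates". It gives no range of event rates, success threshold or assumed true ratio next to that claim.

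SAP section 8.5 reads "A minimum sample size of 1250 subjects will be randomized in the trial up to a maximum of 1550 randomized subjects", and the rest of that section is blacked out.

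Protocol section 4.3.1 defines the endpoint: "The primary effectiveness endpoint is the composite rate of ischemic stroke or systemic embolism at 24 months". Protocol section 15.4 gives the null hypothesis as "p_{\text{WAVECREST}} / p_{\text{CONTROL}} \geq 1.75", with redacted text just before it.

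Protocol section 15 says that the separate SAP is a document "which supersedes this summary". In SAP section 8.3 the non-inferiority hypothesis for effectiveness is redacted. The hypothesis that can be read there is the superiority one, which is on the difference scale: "p_{\text{WAVECREST}} - p_{\text{CONTROL}} \geq 0.0".

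The Watchman background in Protocol section 2.6 reports, for an earlier trial, that "ischemic stroke or systemic embolism beyond 7 days post-randomization occurred at a rate of 0.0253 subject-years in the intervention group".

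**The concern.** On a ratio scale, power is driven by the number of events. With a cap of 1,550 subjects there must be some event rate below which power drops under 80%, yet the synopsis sentence names no floor. Excluding a ratio of 1.75 when the true ratio is 1 takes about 100 events at one-sided 2.5%. The quoted Watchman rate, read as an 18-month cumulative risk, yields about 52 events over 24 months.

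If that were the design, the main power statement for a co-primary hypothesis would be well off. Trial success also requires safety to pass (Protocol section 15.8), so joint power could be no higher. An inconclusive result would then be read against a promise that the trial could not keep.

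**Working it through.** **The plan's own figure.** The 80% cannot be reproduced. Protocol section 15.7 (power and adaptive sample size) is in the table of contents but not in the published body. SAP section 8.5 is redacted after one sentence. The SAP appendix of operating characteristics is listed but not shown. Only a conditional check is possible.

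**Inputs from the documents.** N = 1,550 (775 per arm) or 1,250 (625 per arm); ratio margin 1.75, ln(1.75) = 0.5596; rate 0.0253; accrual 2 to 3 years; follow-up to 5 years.

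**Assumptions.** True ratio 1; one-sided error of 2.5% or 5% (z = 1.960 or 1.645).

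**Events needed for 80% power.** 4(z_a + 0.842)² / 0.5596² = 100.3 at 2.5% and 79.0 at 5%.

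**Two readings of 0.0253.** The text calls it an 18-month event rate but expresses it in subject-years.
- 18-month cumulative: 1 − (1 − 0.0253)^(24/18) = 3.36% at 24 months; hazard −ln(0.9747)/1.5 = 0.0171 per year.
- Per subject-year: 1 − exp(−2 × 0.0253) = 4.93% at 24 months.

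**24-month data only.** SE of the log risk ratio = √(2(1 − p)/(np)); power = Φ(0.5596/SE − z_a).
- p = 3.36%: SE = 0.2725; 0.5596/0.2725 = 2.054; Φ(2.054 − 1.960) = 54%; Φ(2.054 − 1.645) = 66%.
- p = 4.93%: SE = 0.2230; 0.5596/0.2230 = 2.509; Φ(0.549) = 71%; Φ(0.864) = 81%.

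A posterior-probability simulation with a Jeffreys prior agrees: 53% and 65% at 3.36%, 68% and 80% at 4.93%, for thresholds 0.975 and 0.95.

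**First week.** The quoted figure counts only events after day 7; the present endpoint has no such exclusion. The protocol reports 2.2% for a wider first-week composite in the same earlier trial, without the stroke and embolism part. I assume 0.7–1.0% and add it to each 24-month rate.

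**All follow-up to the last subject's month 24.** SAP section 8.7.2 names a Bayesian piecewise exponential model for the later time points; such a model can use follow-up beyond 24 months. With accrual uniform over A = 2 or 3 years, follow-up t runs from 2 to 2 + A years. With hazard λ and attrition w = 0 or 5% per year, events D = 1,550 × λ/(λ + w) × the mean of 1 − exp(−(λ + w)t). Power = Φ(0.5596 × √D/2 − z_a). Example: λ = 0.0253, A = 2, w = 0 gives D = 113.1 and Φ(2.976 − 1.960) = 85%.

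| Data used (N = 1,550) | Rate | Events | Power, 2.5% | Power, 5% |
|---|---|---|---|---|
| 24 months, 18-month reading | 3.36% | 52 | 54% | 66% |
| same, first week added | 4.06–4.36% | 63–68 | 62–65% | 73–76% |
| 24 months, per-year reading | 4.93% | 76 | 71% | 81% |
| same, first week added | 5.63–5.93% | 87–92 | 77–79% | 85–87% |
| all follow-up, 18-month reading | 0.0171/yr | 72–90 | 66–76% | 77–84% |
| all follow-up, per-year reading | 0.0253/yr | 105–131 | 82–89% | 89–94% |

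At N = 1,250 with 24-month data, power is 45% / 58% at 3.36% and 62% / 73% at 4.93%.

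**Scale of the margin.** The argument that power falls with the event rate holds for a ratio margin. For a difference margin the reverse is true. The margin needed for 80% power at one-sided 2.5% is 2.80 × √(2p(1 − p)/775), which is 2.6 percentage points at 3.36% and 3.1 at 4.93%. A fixed difference margin therefore becomes easier to meet as the rate falls. Since the governing SAP hypothesis is hidden and its visible companion is a difference, a second or different margin cannot be ruled out.

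**The case for a change.** The best case for the concern is that it does not depend on the redactions. With a ratio margin and a cap on N, a floor rate exists, and the synopsis omits it. With 24-month data at one-sided 2.5%, power at 0.0253 as quoted stays below 80% at N = 1,550 under either unit and every formula tried (49–71%). Even the wider Watchman composite of 0.03 per subject-year, or 1 − exp(−0.06) = 5.82%, gives at most 78%. To reach 80% the design needs a higher rate, a looser threshold, longer follow-up or some mix of these, and the sentence names none of them.

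Two things stand. The arithmetic is right under its conditions, and the sentence is brief: it does not say whether 80% is joint or per endpoint.

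The step from there to a wrong figure fails. The sentence claims 80% over a range of rates, and that range is not visible. The 0.0253 comes from another trial and is nowhere given as a design assumption. The 54% result combines the lower unit reading, no first-week events, follow-up cut at 24 months and the stricter error level. Relaxing these within what the documents allow takes the answer past 80%. Printing a floor of 5% or 6%, or calling 3.4% the Watchman rate, could itself put a wrong number into the plan.

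**Conclusion.** The concern does not hold. Depending on the unit of 0.0253, the first week, the follow-up analysed and the error level, effectiveness power at N = 1,550 runs from 54% to 94% in the table above, on both sides of the stated 80%. The documents do not fix which row applies, because the threshold, event-rate range, adaptive rule, operating characteristics and SAP non-inferiority hypothesis are withheld from the public copy. Withheld text is not a gap in the plan.

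This rests on a true ratio of 1, error levels of 2.5% and 5% in place of the hidden threshold, uniform accrual and 0–5% attrition per year for the all-follow-up rows, and an assumed 0.7–1.0% for the first week. It does not confirm the 80%; the figure can be neither reproduced nor refuted from what is public. Safety power and joint power were not checked, for the same reason.

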### 1.3 Regulatory History

Coherex’s WaveCrest device and Boston Scientific’s Watchman device are both CE marked. The Watchman device is approved for commercial use in the United States by the FDA. The WaveCrest device is not approved for commercial use in the United States.

#### The WAVECREST 2 Trial

Trial Title	W AveCrest V s. Watchman Transcatheter LAA C losure to R educe AF-Mediated S Troke 2
Investigational Device Exemption (IDE) Number	G150257
Clinical Investigational Plan Number	CHX_IP014
Revision Number	Rev H
Date	04 December 2019

## 2. BACKGROUND AND JUSTIFICATION FOR CLINICAL TRIAL

This document is a Clinical Investigational Plan (CIP) for the WAVECREST 2 Investigational Device Exemption (IDE) trial. The WAVECREST 2 trial is a prospective, multicenter, randomized, active control, clinical trial to evaluate safety and effectiveness of the Coherex WaveCrest® Left Atrial Appendage (LAA) Occlusion System in subjects with non-valvular atrial fibrillation at increased risk for stroke or systemic embolism who have an appropriate rationale to seek a non-pharmacologic alternative to chronic oral anticoagulation by demonstrating that the device is non-inferior to the Watchman® device with respect to the primary safety and effectiveness endpoints.

Normal heart contractions begin as electrical impulses in an area of the right atrium called the sinoatrial node. As an impulse travels through the atria, it produces a coordinated atrial muscular contraction that pumps blood through the atrioventricular (AV) valves into the ventricles. The electrical impulse passes to the AV node in the muscle wall between the two ventricles, producing a coordinated ventricular muscular contraction that pumps blood to the lungs and the systemic circulation. This orderly process is repeated billions of times in a normal lifetime.

Atrial fibrillation (AF) is the most common sustained cardiac arrhythmia affecting an estimated 2.3 million individuals in the USA. AF is usually associated with underlying heart disease (of

	Title: The WAVECREST 2 Trial  Clinical Investigational Plan	Doc. #: CHX_IP014	Rev: H
---	--	-----------------------------	------------------

almost any cause) that may result in multiple electrical atrial impulses. These impulses arise from and travel through the atria at different times, producing disorganized, chaotic, and rapid atrial contractions that lead to conduction of irregular impulses to the ventricles. The atria become ineffective, dilated, and the normal flow of blood through them is significantly altered.

Atrial fibrillation is classified as valvular and non-valvular. Non-valvular AF refers to cases without rheumatic mitral valve disease, prosthetic heart valve, or valve repair. Non-valvular AF can be further classified according to the AHA/ACC/ESC guidelines as paroxysmal, persistent, and/or permanent. Paroxysmal AF has been reported in an estimated 25 to 90% of patients with AF although 90% of cases of paroxysmal AF are asymptomatic and therefore the prevalence may not be known.

The alteration in blood flow in AF patients has adverse consequences related to a reduction in cardiac output and to atrial and LAA thrombus formation that can lead to systemic embolization including stroke. Thrombus may form within the LAA perhaps because of its shape and trabeculations, which predispose to blood stasis. Echocardiography and autopsy studies have shown that the LAA is the source of thrombi in more than 90% of non-valvular AF patients who experience stroke.

Atrial fibrillation is responsible for 15% to 20% of ischemic stroke. AF accounts for one-fourth of all strokes in the elderly and is responsible for 70,000 strokes per year in the United States (AHA statistics). The risk of stroke in patients with non-valvular AF is approximately 5% per year in patients over age 76. Based on risk factors and treatment or the lack thereof, the risk of stroke can be as high as 18.2% per year in select patient populations.

## 2.1 Oral Anticoagulant Therapy

Guidelines recommend chronic anticoagulation for patients with non-valvular AF at risk of stroke. Anticoagulation therapy with the Vitamin K antagonist, warfarin, has been shown to lower the risk of clinical thromboembolism in virtually all patients with AF, including all levels of risk, and irrespective of type (paroxysmal, persistent, or chronic/permanent). Despite its proven efficacy, warfarin is often not well tolerated by patients and has a narrow therapeutic range and high risk of bleeding complications. Patients on long-term warfarin also experience numerous drug-drug, drug-supplement, and drug-food interactions and need frequent international normalized ratio (INR) assessments. Only about 50% of patients who are eligible for long-term warfarin are treated with it.a,27,28 One review of antithrombotic therapy in high-risk AF patients before admission for stroke (Registry of the Canadian Stroke Network) revealed that 29% of patients were not receiving any antithrombotic therapy, and only about one quarter of the 39% receiving warfarin (i.e., 10% of acute stroke patients with known AF) achieved therapeutic INR levels. In a recent large national assessment of warfarin therapy use involving 138,319 subjects in the US and 2,683,674 INR results, the reported mean time in therapeutic range was only 53.7%. Additionally, approximately 20% of patients with AF in whom

a Approved FDA Medication Guide found at:  
<http://www.fda.gov/downloads/Drugs/DrugSafety/ucm088578.pdf>

warfarin is recommended have a contraindication to warfarin (e.g., systemic or intracranial bleeding, potential for non-compliance with therapy, pregnancy, hypersensitivity).

Randomized trials of novel anticoagulants (NOACs) such as direct thrombin inhibitor (dabigatran), and direct factor Xa inhibitors (apixaban, rivaroxaban, edoxaban) against warfarin have demonstrated a reduction in thrombotic and hemorrhagic stroke when compared with warfarin. NOACs have a more predictable pharmacokinetic profile than warfarin, fewer drug-drug and drug-food interactions, and do not require INR assessments. NOACs have also generally demonstrated a significant reduction in major bleeding when compared with warfarin, including an important reduction in intracranial hemorrhage. Several NOACs have received market approval for stroke risk reduction in non-valvular AF patients. However, bleeding related to the use of NOACs remains a clinically significant issue. This bleeding risk increases with age, decreased creatinine clearance and concomitant aspirin use. The randomized NOAC trials also reported significant discontinuation rates for both NOACs and warfarin (>20% at 2 years). The fundamental challenge in AF patients is long-term stroke prevention with no significant increased risk of major bleeding.

**2.2 Risk-Stratification**

Decision-making regarding the initiation of anticoagulant medication requires tools to predict both embolic and bleeding risk. Risk stratification for embolization in patients with non-valvular AF can be performed using both clinical and echocardiographic parameters. These parameters have been derived from both randomized trials and community cohorts. To identify AF patients at risk for stroke, the Atrial Fibrillation Investigators (AFI) pooled and analyzed data from five randomized stroke prevention trials in subjects with non-valvular AF. The resulting CHADS2 scoring system^41 has until recently been recommended for use to estimate embolic stroke risk in AF patients. CHADS2 is an acronym created from the first letter of five clinical parameters: **C**ongestive heart failure, **H**ypertension, **A**ge ≥ 75 years, **D**iabetes mellitus, and prior **S**troke/TIA/Thromboembolism. The CHADS2 score ranges from 0 to 6. A limitation of the CHADS2 score is that a subset of patients with a CHADS2 score of 1 may have other risk factors for embolic stroke that are not accounted for. This limitation is overcome by the use of the CHA2DS2-VASc score (which gives an additional point each for Vascular disease, Age 65 to 74 years, and female Sex). The CHA2DS2-VASc score ranges from 0 to 9. The CHA2DS2-VASc scoring system can be used to reliably identify truly low risk patients, who can be managed without antithrombotic therapy (i.e., patients with CHA2DS2-VASc score of 0). **Appendix II** explains the CHADS2 and CHA2DS2-VASc scoring systems.

Table 1 shows stroke risks for the CHA2DS2-VASc scoring system.

